### **3. GENERAL STATISTICAL METHODS**

#### **3.1. Sample Size Justification**

Approximately 50 subjects will be enrolled. The primary endpoint analysis will consist of a log-rank test of the difference in treatment groups in the time to viral clearance. Based on a recent publication

(<https://www.sciencedirect.com/science/article/pii/S2095809920300631?via%3Dihub>),

it is assumed that the median time to clearance for favipiravir would be approximately 4 days, and the median time for placebo would likely be approximately 11 days. This latter estimate may be conservative since SOC is not as likely to reduce viral load as well as the control in the above referenced study. Using two-sided alpha of 0.10 and power of 90% (appropriate for a trial to be used as the justification for a confirmatory, fully-powered, blinded and randomized Phase 3 study), and a fixed per-subject observation period of 15 days, an approximate sample size of 25 subjects per arm (total size of 50) is required.

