### **3.5. Baseline Definitions**

For all analyses, baseline will be defined as the most recent measurement prior to the first administration of study drug for patients on favipiravir. For patients on SOC, baseline will be defined as the closest (either before or after) measurement to randomization.

For the purpose of time-to-event analyses, treatment start date is used as the origin point for patients on favipiravir, while randomization date is used for patients on SOC.

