## 3.11. Visit Windows

It is expected that all visits should occur according to the protocol schedule. However, analysis visits will be derived based on study day for all by-visit summaries and analyses. Analysis visit designations are detailed in [Table 3-1](#).

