### **4.3. Efficacy Evaluation**

#### **4.3.1. Analysis of the Primary Efficacy Endpoint**

The primary endpoint of time to viral clearance will be analyzed with the log-rank test for treatment difference based on a two-sided alpha-level of 0.10 and summarized using Kaplan-Meier methodology. The time to viral clearance (in days) is defined as the time of Negative or Lower Limit of Quantification (LLOQ) results (without any quantitative results after that) as measured by PCR for SARS-CoV-2 via scheduled nasopharyngeal and oropharyngeal swab samples minus the date of first dose + 1.

Subjects who have no evidence of viral clearance will be censored at the time of the last PCR measurement with the following conditions:

- Patients whose symptoms worsen (defined as an increase of  $\geq 1$  point on the 6-point Ordinal Scale from baseline) on the day of the last PCR measurement, or who die will be censored at Day 29,
- Patients who are lost to follow-up will be censored on the day of the last PCR measurement.

The median time to viral clearance will be estimated based on the Kaplan-Meier estimator; additional summary statistics will be presented, including the 25th and 75th percentiles, 90% CIs (the log-log transformation) on the median and other percentiles and proportion of censored subjects. Viral clearance rates at Days 3, 8, 11, 15, and 29 will also be presented.

The analysis of the primary efficacy endpoint will be done using the ITT population.

The primary analysis will be supplemented with a sensitivity analysis, using a stratified log-rank test, where the treatment difference based on a two-sided alpha-level of 0.10 will be summarized and stratified by disease severity.

The analysis will also be repeated by the dexamethasone usage subgroup, where patients will be categorized as having received dexamethasone if they received it at any time prior to the last viral clearance assessment.

Kaplan-Meier curves will be provided for the overall ITT population. By-subject data listings of viral clearance data will also be provided.

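### Uncleared deaths and worsened subjects are censored at Day 29, but a compliant Day 29 swab can fall on Day 30 or 31, so the end of the primary Kaplan-Meier curve overstates clearance

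*SAP*

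**What the plan says.** SAP 4.3.1 measures clearance in actual days, as the time of the qualifying result from "swab samples minus the date of first dose + 1". SAP 3.5 adds that "treatment start date is used as the origin point for patients on favipiravir, while randomization date is used for patients on SOC".

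The default censoring rule is that "Subjects who have no evidence of viral clearance will be censored at the time of the last PCR measurement". Two groups are excepted: subjects at least one category worse than baseline on the ordinal scale on the day of their last PCR, "or who die will be censored at Day 29".

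Protocol Section 13 and SAP Table 1-1 allow the Day 29 visit two days either side, so Days 27 to 31 are compliant. No swab is scheduled between Day 15 and Day 29. SAP Table 3-1 maps Days 25 to 33 to the Day 29 analysis visit, and SAP 3.11 gives its scope: "analysis visits will be derived based on study day for all by-visit summaries and analyses".

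The planned outputs are the log-rank test, the Kaplan-Meier curve with its median and quartiles, and a further item: "Viral clearance rates at Days 3, 8, 11, 15, and 29 will also be presented". Nothing in the SAP stops the clearance clock at Day 29 or moves a Day 30 or 31 swab back to Day 29.

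**The concern.** Holding uncleared deaths to a late fixed day, rather than to their last swab, keeps them in the denominator while survivors go on clearing. Here the fixed day is the centre of the last swab window, not its end. A survivor whose compliant Day 29 visit falls on Day 30 or 31 and who is then first negative counts as an event after every uncleared death, and every subject worsened at the last PCR, has left the risk set. Kaplan-Meier then treats those subjects as if they would have cleared at the survivors' rate.

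Because there is no scheduled swab between Day 15 and Day 29, late clearances concentrate at this visit. At stake are the end of the primary curve, the 75th percentile when it falls at that visit, and the last few terms of the log-rank statistic.

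**Working it through.** **The plan's own figure.** SAP 3.1 assumes that "the median time to clearance for favipiravir would be approximately 4 days", with 11 days for control, two-sided alpha 0.10, 90% power and 15 days of observation. With exponential times the hazard ratio is 4/11 = 0.364.
- Clearance by Day 15 is 1 − 2^(−15/4) = 0.926 and 1 − 2^(−15/11) = 0.611, mean 0.769.
- Freedman's formula needs 39.3 events: 39.3 / 0.769 = 51.2, or 26 per arm.
- Schoenfeld's needs 34: 34 / 0.769 = 44.2, or 46 in total.

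The stated 50 lies between the two. The point does not depend on it.

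**Where the late visit matters.** Under the same assumption, SOC clearance is 1 − 2^(−15/11) = 61% by Day 15 and 1 − 2^(−29/11) = 84% by Day 29. The SOC 75th percentile can therefore fall at the Day 29 visit. Both assumed medians come well before it.

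**Worked arm of 25 (assumed counts).** 15 clear by Day 15, 3 die uncleared, 2 clear on Day 29, 3 clear on Day 31, and 2 are still positive on Day 31.
- Not cleared after Day 15: 10/25 = 0.40.
- Day 29, with 10 at risk (censoring at a tied time follows events): 0.40 × 8/10 = 0.32, so 68% cleared under either rule.
- Day 31 as written, 5 at risk and 3 events: 0.32 × 2/5 = 0.128, so 87.2% cleared.
- Day 31 with deaths held to Day 33, 8 at risk: 0.32 × 5/8 = 0.20, so 80.0% cleared, which is the observed 20/25.

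The excess is 7.2 points.

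**75th percentile (assumed counts).** Of 25, 15 clear by Day 15, 4 die uncleared, and 3 of the 6 survivors clear on Day 30. As written, 0.40 × 3/6 = 0.20 remain uncleared, so the percentile is Day 30. With deaths retained, 0.40 × 7/10 = 0.28 remain, so it is not reached.

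**Simulation.** 25 per arm, exponential clearance, swabs on Days 3, 8, 11 and 15 plus one uniform on Days 27 to 31, deaths uniform over Days 3 to 28, 4,000 replicates. Mortality, death times and swab-day spread are assumptions.

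| Medians (fav, SOC) | Deaths (fav, SOC) | SOC curve end: Day 29 v Day 33 censoring | Log-rank rejection: Day 29 v Day 33 |
|---|---|---|---|
| 4, 11 | 10%, 10% | 92.2% v 86.6% | 91.7% v 90.2% |
| 11, 11 | 10%, 10% | 92.1% v 86.5% | 10.9% v 10.5% |
| 11, 11 | 20%, 20% | 90.9% v 81.0% | 9.8% v 10.0% |
| 11, 11 | 5%, 20% | 90.4% v 80.5% | 11.5% v 13.7% |

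In the first row the favipiravir curve ends at 98.5% v 97.5%.

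Further simulations on similar assumptions gave:
- **Power at the planning medians:** 91.1% v 90.1% and 90.1% v 88.3%.
- **SOC 75th percentile:** it changed in about 10 to 24% of trials in one set of runs. Across all runs the range was 4 to 28%, depending mainly on assumed mortality.
- **Log-rank direction:** with equal medians of 11 and deaths of 5% v 20%, mean Z against the higher-mortality arm was 0.26 as written and 0.45 with Day 33 censoring. With 10% v 20% it was 0.16 v 0.27.

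**The case against.** The strongest reply is that the primary inference hardly moves. Medians before Day 29 and the Kaplan-Meier value at exactly Day 29 do not depend on this choice. Type I error with equal mortality is unchanged, and in simulation the two censoring days gave the same significance decision in 95 to 98% of trials. That stands, and it confines the point to the tail.

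Four stronger readings are tempting, and the documents do not support them.

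- **The rule is reversed.** A reader might infer that the arm with more deaths ends up looking better in the log-rank test. Within the risk sets after Day 29 it does gain, but those hold only about 6 to 11% of events. Overall, mean Z still runs against that arm, so the penalty is diluted and not reversed. The SAP also states no purpose for the rule.
- **The reported Day 29 rate is too low.** This would follow if the rate were read off the curve at t = 29. SAP 4.3.1 does not say so. If the rate is a by-visit summary, Table 3-1 counts swabs through Day 33 and the shortfall disappears.
- **The window runs to Day 33.** Table 3-1 governs by-visit analyses. For the time-to-event analysis the firm limit is the protocol's Day 31, although a later swab would still count on its actual day.
- **The curve can reach 100% when the observed share is 84%.** The arithmetic works for 25 subjects with 17 cleared by Day 15, 4 uncleared deaths and 4 survivors all first negative on Day 30. That is an extreme configuration, not a typical one.

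Finally, if Day 29 meant the nominal visit for every swab, events and censoring would tie at 29 and the problem would vanish. The date-based definition does not say that.

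**Conclusion.** The point holds for the end of the curve. Read as written, SAP 4.3.1 removes uncleared deaths and subjects worsened at their last PCR before compliant swabs on Days 30 and 31 can count. The SOC curve then ends about 6 points too high at 10% mortality (92.2% v 86.6%) and about 10 points at 20% (90.9% v 81.0%), with a median of 11 days. The 75th percentile is sometimes affected. Log-rank power changes by about 1 to 2 points.

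These sizes rest on assumed mortality and on swab days spread evenly over Days 27 to 31, which puts two-fifths of them after Day 29. Fewer late visits would shrink the effect. Worsened subjects were not simulated, so the reach of the rule is somewhat wider than the figures show.

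Day 33 censoring removes only the part due to this rule. In the first scenario the SOC curve still ends at 86.6% against an observed share of 80.3%, because surviving uncleared subjects are censored on their own swab dates.

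This is a modest misalignment in the one analysis that the SAP does not label descriptive. It is worth correcting but does not threaten the primary test.

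**What to change.** In SAP 4.3.1, replace Day 29 as the censoring time for both groups (deaths without clearance, and subjects worsened on the day of the last PCR) with a common time no earlier than the last swab that can count as the Day 29 assessment. Day 33, the end of the Table 3-1 window, would serve. State that limit for the time-to-event analysis, and report the Day 29 clearance rate over the same window so that the curve and the rate agree.

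Assigning every swab its scheduled visit day is not an equivalent route. It changes all event times, and it gives no day for the discharge swabs that Protocol 9.6 includes in this analysis.

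The cost is a short SAP wording change, best settled before the analysis is run. It needs no new data and does not alter the sample size.

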 - i. Fever ≤ 37.2 °C oral,
 - ii. Respiratory rate ≤ 24 /minute on room air,
 - iii. Oxygen saturation SpO2 > 94% on room air,
 - iv. Cough mild or absent on a patient reported scale of severe, moderate, mild, absent.
- 3. Clinical effect as measured by the National Early Warning Score 2 (NEWS2) system.
- 4. All-cause mortality as assessed daily up to 29 days and at final follow up on Day 60.
- 5. Frequency of respiratory progression as assessed up to 29 days (daily and per SOC at each site) and defined as:
 - a. SpO2 \leq 94% on room air or PaO2/FiO2 \leq 300mmHg, and
 - b. requirement for supplemental oxygen, or
 - c. more advanced ventilator support.
- 6. Time to defervescence (in those with fever at enrollment) as assessed daily up to 29 days and at Day 60 (if possible).
- 7. Time to cough reported as mild or absent (in those with cough at enrollment rated severe or moderate) as assessed daily up to 29 days and on Day 60.
- 8. Time to dyspnea reported as mild or absent (on a scale of severe, moderate, mild absent, in those with dyspnea at enrollment rated as severe or moderate) as assessed daily up to 29 days and on Day 60 (if possible).
- 9. Frequency of requirement for supplemental oxygen or non-invasive ventilation as assessed daily up to 29 days and on Day 60.
- 10. Time to SARS-CoV-2 RT-PCR negative in upper respiratory tract specimen as assessed up to 29 days.
- 11. Change in SARS-CoV-2 viral load in upper respiratory tract specimen as assessed by area under viral load curve as assessed up to 29 days.
- 12. Frequency of requirement for mechanical ventilation as assessed up daily to 29 days and at Day 60
- 13. Safety of favipiravir + SOC v. SOC alone as assessed daily up to 29 days and at Day 60.
- 14. C-reactive protein (CRP) over time.
- 15. Population PK analysis of favipiravir with assessment of maximum plasma concentration (C_{max}), minimum plasma concentration (C_{min}), and AUC_(0-24h) on Days 1, 2, 8 and 14.

Study Sites	Approximately 8 sites in the U.S.A.
Planned Enrollment	Approximately 50 subjects; randomized 1:1
Study Population	Adults who are hospitalized for treatment of confirmed COVID-19

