8 EFFICACY, PHARMACOKINETICS AND SAFETY ASSESSMENTS

8.1 Efficacy Assessments

Efficacy will be assessed by the following measurements:

- Presence of virus in the nasopharyngeal and oropharyngeal samples taken on Days 1, 3, 8, 11, 15 and 29 (if hospitalized and when able to return to clinic after discharge). Swabs will also be obtained on day of discharge from hospital if discharge occurs before Day 15.
- Clinical improvement of hospitalized subjects with COVID-19 receiving either favipiravir + SOC or SOC alone as defined by the following study-specific 6-point ordinal scale at Day 15

- 1. Not hospitalized
- 2. Hospitalized, not requiring supplemental oxygen
- 3. Hospitalized, requiring supplemental oxygen
- 4. Hospitalized, on non-invasive ventilation or high flow oxygen devices
- 5. Hospitalized, on invasive mechanical ventilation or ECMO
- 6. Death
- Status on the study specific 6-point ordinal scale assessed daily while hospitalized and at each outpatient visit until Day 60.
- NEWS2 assessed daily while hospitalized and at each outpatient visit until Day 60.
- Patient status assessed daily while hospitalized and at each outpatient visit until Day 60 via Study-specific Symptom Status and the ECOG Performance Status questionnaires (see Appendix A).
- Duration of supplemental oxygen (if applicable).
- Duration of mechanical ventilation (if applicable).
- Duration of hospitalization.
- Date and cause of death (if applicable).
- PCR and TCID50 in nasopharyngeal and oropharyngeal swabs on Days 1, 3, 8, 11, 15 and 29 (if hospitalized and when able to return to clinic after discharge), and on day of discharge if hospital discharge occurs before Day 15.
- Blood for determination of antibodies to SARS-CoV-2 obtained on Days 1, 15 and 29 (if hospitalized and when able to return to clinic after discharge).

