9.2 Sample size justification

Approximately 50 subjects will be enrolled. The primary endpoint analysis will consist of a log-rank test of the difference in treatment groups in the time to viral clearance. Based on a recent publication:

(https://www.sciencedirect.com/science/article/pii/S2095809920300631?via%3Dihub)

it is assumed that the median time to clearance for favipiravir would be approximately 4 days, and the median time for SOC would likely be approximately 11 days; this latter estimate may in fact be conservative since SOC is not as likely to reduce viral load as well as the control in the above referenced study. Using two-sided alpha of 0.10 and power of 90% (appropriate for a trial to be used as the justification for a confirmatory, fully-powered blinded and randomized Phase 3 study), and a fixed per-subject observation period of 15 days, an approximate sample size of 25 subjects per arm (total size of 50) would be required.

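### The planned Kaplan-Meier medians for viral clearance are drawn to swab days and run late; an interval-censored estimate should sit beside the unchanged log-rank test

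*SAP*

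**What the plan says.** Protocol 8.1 measures virus in nasopharyngeal and oropharyngeal "samples taken on Days 1, 3, 8, 11, 15 and 29". The Schedule of Assessments allows one day either side at Days 3, 8 and 11, minus 1 to plus 2 days at Day 15, and two days either side at Day 29. A further swab is taken at discharge if that falls before Day 15 (Protocol 7.7 and 8.1).

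SAP 4.3.1 takes the event time as the date of the negative or below-LLOQ PCR result with no quantifiable result afterwards, minus the first-dose date, plus one. The test is a log-rank test at two-sided 0.10. For estimation, "The median time to viral clearance will be estimated based on the Kaplan-Meier estimator", with quartiles and 90% CIs. Clearance rates at Days 3, 8, 11, 15 and 29 are also reported. No interval-censored or grouped-time estimate and no hazard ratio is planned for this endpoint.

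The two documents differ on the discharge swab. Protocol 9.6 puts it in the clearance analysis, while the definition in SAP 4.3.1 refers to scheduled swabs.

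For the active arm, the sizing in Protocol 9.2 reads "it is assumed that the median time to clearance for favipiravir would be approximately 4 days". Its figure for the control arm is given as follows: "the median time for SOC would likely be approximately 11 days". The follow-up used in that calculation is "a fixed per-subject observation period of 15 days".

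**The concern.** A subject who is positive on Day 3 and negative on Day 8 cleared at some point in between, but the analysis records Day 8. On the nominal schedule these gaps are 2, 5, 3, 4 and 14 days. A Kaplan-Meier curve built on swab dates can step only on those dates, so its percentiles and their confidence limits mostly reflect the visit calendar.

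At stake is the one planned estimate of the primary endpoint on the time scale. Protocol 9.1 says the study should support Phase 3 by describing the treatment effect on time to viral clearance. A reader who sets the reported medians against the 4 v 11 days used for sizing may be comparing different quantities.

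**Working it through.** **Inputs.** Medians of 4 and 11 days, "Using two-sided alpha of 0.10 and power of 90"%, 15 days of observation (Protocol 9.2); 1:1 allocation (Synopsis); swab days from Protocol 8.1; event-time rule from SAP 4.3.1. Assumed here: exponential times, a perfect assay and no rebound.

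**1. The plan's sample size.** The ratio of medians is 11/4 = 2.75.
- Proportion cleared by 15 days, 1 − 2^(−15/m): 0.926 for m = 4 and 0.611 for m = 11; mean 0.7685.
- Freedman events: (1.645 + 1.282)² × (3.75/1.75)² = 8.564 × 4.592 = 39.3, so 40. Unrounded, N = 39.3/0.7685 = 51.2; power at N = 50 is 0.894.
- Exponential rate-difference formula: 25.3 per arm.
- Schoenfeld: 34 events, N = 45, power 0.932 at N = 50.

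The stated 25 per arm is reproduced to within about two subjects by the first two methods. All three treat clearance times as continuously observed.

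**2. What Kaplan-Meier would report.** With elapsed time t = study day − 1, the proportion cleared by a swab day is 1 − 2^(−t/m).

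| Swab day (t) | 3 (2) | 8 (7) | 11 (10) | 15 (14) | 29 (28) |
|---|---|---|---|---|---|
| Favipiravir, m = 4 | 0.29 | 0.70 | 0.82 | 0.91 | 0.99 |
| SOC, m = 11 | 0.12 | 0.36 | 0.47 | 0.59 | 0.83 |

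The median is the first swab day at which the proportion reaches 0.50: Day 8 and Day 15.

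**3. Splitting the shift.** On the plus-one scale the true medians are study days 5 and 12. Each arm therefore moves one day from the day count (4 to 5, 11 to 12) and three from the schedule (5 to 8, 12 to 15). The ratio goes from 2.75 to 12/5 = 2.40 and then to 15/8 = 1.88. The 7-day difference survives only by coincidence. If elapsed time is instead set equal to study day, favipiravir is at 0.75 by Day 8 and SOC at exactly 0.50 by Day 11, so the SOC median falls on Day 11 or Day 15.

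**4. How little the reported value says.** Any true median above 2 and up to 7 days reads Day 8; any above 10 and up to 14 reads Day 15. A reported 8 v 15 therefore fits gaps from just over 10 − 7 = 3 to just under 14 − 2 = 12 days.

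**5. Sampling variation, 25 per arm, complete swabs.** The median falls on the first swab day by which at least 13 of 25 have cleared. For favipiravir, P(Day 8) = P(Bin(25, 0.703) ≥ 13) − P(Bin(25, 0.293) ≥ 13) = 0.984 − 0.014 = 0.970. For SOC the same calculation gives Day 8, 11, 15 and 29 with probabilities 0.07, 0.30, 0.44 and 0.19. True favipiravir medians of 3 and 5 days would still read Day 8 in 91% and 89% of trials.

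**6. Simulation with the actual swab rules** (1,500 trials per scenario, follow-up to Day 29; interval-censored exponential medians from 400). The third scenario assumes discharge on Days 4–21 and 60% attendance afterwards; neither figure is in the documents.

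| Scenario | Middle KM medians | Interval-censored medians (days) | Log-rank rejection: swab grid v continuous |
|---|---|---|---|
| Nominal days | 8 v 15 | 4.0 v 11.0 | 0.946 v 0.955 |
| Visit windows | 8 v 15 | 3.9 v 10.7 | 0.927 v 0.957 |
| Windows, discharge swabs, missed visits | 8 v 15 | 3.9 v 10.9 | 0.895 v 0.963 |

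With no treatment effect the log-rank test rejected in 0.10 to 0.11 of trials in all three scenarios.

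**The case against.** The endpoint is defined as the day of a negative result, and Kaplan-Meier is a coherent summary of that. Proof of concept rests on a significant log-rank test (Protocol 9.1), which the grid barely touches. Visit-day clearance rates do not depend on the unseen clearance date, and SAP 4.3.2.9 adds quantitative viral-load analyses. All of this stands, but none of it corrects the medians, quartiles or their intervals.

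The 4 and 11 days may themselves be swab-based. They come from a publication whose timing rule the documents do not give, and Protocol 2.6 calls them means where 9.2 calls them medians. This stands too. The 8 v 15 result is conditional on reading them as true clearance times.

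Recovering 4 and 11 with an exponential model from exponential data is partly circular, and a nonparametric estimate cannot place the median inside a swab gap without interpolation. That is also correct, and it is the price of the remedy.

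Three stronger readings are tempting:
- That clearance can be seen only on five fixed days. It cannot be put that way: the visit windows and the discharge swab add dates. They spread the reported values but left the middle medians at Day 8 and Day 15 under the assumed patterns.
- That the primary test is compromised. With one schedule in both arms it is not. If discharge timing differed by arm in this open-label trial, swab timing would differ too, but the documents give no figures from which to size that.
- That Phase 3 will be sized on these medians. Protocol 9.1 says only that clearance information supports Phase 3; Protocol 4.2 has the 6-point ordinal scale under assessment as the later trial's primary clinical endpoint.

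**Conclusion.** The point holds for estimation, not for testing. Under the plan's own medians, taken as true exponential clearance times on the nominal schedule, the reported medians are typically Day 8 v Day 15. Their ratio is about 1.9 instead of 2.75, and the pair is compatible with true gaps between 3 and 12 days. About three days of each shift are due to the schedule and one to the day count. The log-rank test keeps its size and loses about 1 point of power on the nominal grid. The loss was about 3 points with visit windows, and about 7 with the assumed discharge and attendance pattern, where missed visits contribute as well as the grid. These figures rest on exponential times, a perfect assay, no rebound and a common schedule in both arms. No claim is made that the Phase 3 trial will be sized on the medians. This is a worthwhile, inexpensive improvement and does not threaten the proof-of-concept decision.

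**What to change.** Leave the log-rank test as primary. In SAP 4.3.1:

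1. Label the Kaplan-Meier median and quartiles as day of first sustained negative swab.
2. Add a supplementary interval-censored estimate with 90% CIs, using each subject's actual last-positive and first-sustained-negative swab dates. Use nonparametric maximum likelihood, reporting the interval that contains the median, and/or a parametric model with its assumption stated.
3. State that discharge-day swabs are included, in line with Protocol 9.6.
4. State how the Day 29 censoring rule for death or worsening carries over to the interval-censored analysis.
5. Optionally, add an interval-censored log-rank test as a sensitivity analysis.

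The cost is a short SAP addition and a small amount of extra analysis, with no new data collection. The downside is reliance on a modelling or interpolation assumption, which is acceptable for a supplementary estimate if it is declared in advance.
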